8 EFFICACY, PHARMACOKINETICS AND SAFETY ASSESSMENTS

8.1 Efficacy Assessments

Primary Measurement (Efficacy):

1. Nasal swab for PCR taken daily from Day 1 to Day 10, and Days 14, 21, and 28.

Secondary Measurements (Efficacy):

1. Nucleic acid (RT-PCR) from oropharyngeal swabs collected on Days 1, 5, 10, and 28.
2. Symptom improvement or worsening: Subjects will fill in a diary daily, recording the following symptoms:
 - a. Cough/Shortness of breath/dyspnea
 - b. Fatigue
 - c. Headache/Body aches
 - d. Joint pain
 - e. Chest pressure
 - f. GI symptoms including nausea, vomiting, and/or diarrhea
 - g. Abdominal pain
 - h. Sore throat
 - i. Nasal congestion
 - j. Chills
 - k. Runny nose
 - l. Oral temperature taken after 4 pm and at least four hours after ingesting the most recent antipyretic (acetaminophen or NSAID)
 - m.
 - n. New loss of taste or smell
 - o. Abdominal pain
 - p. Rash
3. Blood for determination of antibodies to SARS-CoV-2 will be obtained on Days 1, 14, and 28.
4. Number of subject hospitalizations, emergency department visits, incidence of respiratory failure, deaths, and proportions of subjects alive, not hospitalized, and free of respiratory failure on day 28

8.2 Required Resistance Testing

Resistance testing, as required in clinical trials of anti-viral drugs will be performed at each time point that oropharyngeal swabs are taken.

8.3 Pharmacokinetics/Pharmacodynamics Assessments

6.0mL of blood may be collected for PK obtained pre-dose (within 30 minutes prior to dosing) and post-dose (45 to 75 minutes following dosing) on Days 1, 5 and 10. These collections are optional.

Kits for each PK draw and instructions for handling and shipping are provided by the PK analysis laboratory.

8.4 Safety Assessments

Abnormal clinical laboratory values that are clinically significant and all reported adverse events will be graded according to the Common Terminology Criteria for Adverse Events (CTCAE) version 5.0.

Safety will be assessed by the collection of observed and reported adverse events, physical exams, vital signs and the following clinical laboratory tests:

- **Hematology**

Hemoglobin (Hgb)	Hematocrit (Hct)
Platelet count	Red blood cell count
White blood cell count with differential	

- **Chemistry**

Blood Urea Nitrogen (BUN)	Creatinine
Total bilirubin	Alkaline Phosphatase
Aspartate transaminase (AST)	Alanine transaminase (ALT)
Gamma-glutamyl transferase (GGT)	Albumin
Glucose	Bicarbonate
Total protein	Sodium
Phosphate	Chloride
Potassium	
Calcium	C-reactive protein
Urate	

NOTES:

- All clinical laboratory assessments listed above (hematology and chemistry) will be conducted at the Stanford University Medical Center clinical laboratory.
- If coagulation assays are ordered as part of the SOC, the results should be added to the EDC.

Including PK and Clinical Laboratory Testing, subjects will undergo up to 7 planned venipunctures during this study.

8.4.1 Adverse Events

Treatment-emergent AEs will be defined as those occurring coincident with start of treatment through 28 days post-treatment.

Subjects will be instructed to report AEs during the study and staff will query subjects regarding AEs throughout the study. The Site Investigator (and/or designee) must document all AEs reported through completion of the Day 28 visit. Any subject who is withdrawn from the study due to an AE shall be followed until the event has resolved or stabilized or 14 days after last dose, if in the

favipiravir arm. The Site Investigator will document available follow-up information on the subject's source documentation and CRF

8.4.2 Definition of an Adverse Event

The FDA Safety Guidance, referencing 21CFR312.32(a), defines an Adverse Event as follows:

Adverse event means any untoward medical occurrence associated with the use of a drug in humans, whether or not considered drug related.

An adverse event (also referred to as an adverse experience) can be any unfavorable and unintended sign (e.g., an abnormal laboratory finding), symptom, or disease temporally associated with the use of a drug and does not imply any judgment about causality. An adverse event can arise with any use of the drug (e.g., off-label use, use in combination with another drug) and with any route of administration, formulation, or dose, including an overdose.

Adverse Events are **NOT**:

- **Clinical events related to the progression of COVID-19.**
- Medical or surgical procedures (e.g., surgery, endoscopy, tooth extraction, transfusion). The condition that leads to the procedure is the AE.
- Situations where an untoward medical occurrence has not occurred (e.g., hospitalization for elective surgery, social and/or convenience admissions).

8.4.3 Evaluating and Reporting of Adverse Events

All AEs (i.e. a new event or an exacerbation of a pre-existing condition) that occur after dosing with favipiravir and after completion of baseline assessments in the Placebo + SOC arm, must be recorded as an AE or SAE (if applicable), on the Adverse Event eCRF and SAE form, as applicable. The Site Investigator must follow all AEs until the AE resolves, or until the Site Investigator and/or the Medical Monitor determine the event is chronic or clinically stable. If an AE remains unresolved at the conclusion of the study, the Site Investigator and Medical Monitor will make a clinical assessment to determine whether continued follow-up of the AE is warranted. All subjects who have received at least one exposure to study therapy will be evaluated for safety of study treatment.

The Site Investigator should attempt to establish a diagnosis of the event based on signs, symptoms and/or other clinical information. In such cases, the diagnosis should be documented as the AE and not the individual signs/symptoms.

All AEs must be promptly documented on the Adverse Event eCRF and assessed by the Site Investigator. Details of the event must include the dates of onset and resolution, severity, relationship to study drug, seriousness, and whether the event caused the subject to withdraw from the study, outcome and timing with regard to administration of the study drug.

Severity: Severity should be graded and recorded as follows:

- Mild: Awareness of event but easily tolerated
- Moderate: Discomfort enough to cause interference with usual activity

- Severe: Inability to carry out usual activity, incapacitating, requires medical intervention

Relationship: The relationship of the Adverse Event to the study drug will be determined initially by the Site Investigator, and assessed using the following definitions:

- **Related:** There is a distinct temporal relationship between the event onset and administration of the study drug. There is a known reaction to agent or chemical group or predicted by known pharmacology. The event cannot be explained by subject's clinical state or other factors.
- **Unrelated:** Evidence exists that the AE has an etiology other than the study drug (e.g., pre-existing condition, underlying disease, intercurrent illness, or concomitant medication).

Final determination of relatedness will be made by the Sponsor.

Expectedness: Whether or not the event was expected or unexpected. Further details on this can be found in section 8.5.

These criteria, in addition to good clinical judgment, should be used as a guide for determining the causal assessment. If it is felt that the event is not related to study drug therapy, then an alternative explanation should be provided.

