6 STUDY TREATMENT - FAVIPIRAVIR

6.1 Study Drug

Favipiravir will be provided in 200 mg tablet form to be stored at controlled room temperature (15°C to 30°C [59°F to 86°F]) and shielded from light. Matching placebo will be provided in tablet form to be stored at controlled room temperature (15°C to 30°C [59°F to 86°F]) and shielded from light.

Standard Dose

Subjects randomized to the favipiravir + SOC arm will be administered loading doses of 1800 mg BID (ideally 12 hours apart but 10-16 hours is allowed) on Day 1, and then maintenance dosing of 800 mg twice daily BID (Ideally 12 hours apart but 10- 16 hours is allowed) on Days 2-10 beginning 24 hours after the first dose. Day 1 is deemed to be the first 24 hours after enrollment into the study, with time 0 (time of first dose) occurring as soon as possible after the subject's eligibility has been confirmed.

An exception to the above maintenance dose will be made for those subjects entering the study with a Child-Pugh liver impairment of grade A who will receive favipiravir 600 mg BID on Days 2 through 10.

Subjects randomized to the placebo + SOC arm will be administered placebo BID (ideally 12 hours apart but 10-16 hours is allowed) on Day 1, and then maintenance dosing twice daily BID (Ideally 12 hours apart but 10- 16 hours is allowed) on Days 2-10 beginning 24 hours after the first dose. Day 1 is deemed to be the first 24 hours after enrollment into the study, with time 0 (time of first dose) occurring as soon as possible after the subject's eligibility has been confirmed.

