7.2 Day 1 (FIRST DOSE AND POST-DOSE)

NOTE: Day 1 is deemed to be the first 24 hours after enrollment into the study, with time 0 (time of first dose) occurring as quickly as possible after the subject's eligibility has been confirmed.

- Administer first dose (1800 mg favipiravir or placebo) at time 0.

Following First Dose:

- Monitor patient for 30 minutes after their first dose.
- Optional: Take a blood sample 45 to 75 minutes following the first dose for post-dose PK analysis

7.3 Days 5, 10, 28 (Follow-up) or Early Termination (Window of +1 or -1 day allowed on Days 5 and 28. Window of -1 allowed for Day 10.)

- Conduct and record the results of a Physical Exam (Day 5, 10, 28).
- Review and record concomitant medications (Note: if there have been changes in concomitant medications during the study, determine whether the change is due to an AE).
- Measure and record vital signs (BP, HR, Temp, Resp).
- Collect and record SPO2 by Finger Sensor
- Collect oropharyngeal swab for virologic testing (RT-PCR) and resistance analysis.
- Collect and record adverse events (see Section 8.4 for detailed instructions).
- Collect nasal swab for antigen testing and molecular viability testing (day 1, 5, 10)
- Collect blood samples for:
 - Hematology and clinical chemistry laboratory analyses (Day 5, 10, 28)
 - Urine for repeat pregnancy test (Day 5)
 - Optional: Antibodies to SARS-CoV-2. (28)
 - Optional: Biobanking (28)
 - Optional: Blood for PK and resistance analysis obtained pre-dose (within 30 minutes prior to dosing) and post-dose (45 to 75 minutes following dosing) (Days 5 and 10).
- Optional: Provide Zymo fecal stool collection kit: one on Day 1, two on Day 10, and 28.

- Optional: Collect stool samples on Day 5, 14, 28, and patient sends in sample at 4 months post enrollment date.

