8.4.4 Serious Adverse Events (SAEs)

All SAEs as defined below and that occur after the first dose of favipiravir and up to 46 days post-dose must be reported to the Sponsor as soon as the site becomes aware of them. Any SAEs occurring more than 46 days after last study drug administration and considered at least possibly drug-related must also be reported.

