8.4.6 SAE Reporting Requirements to the Sponsor

The procedure for reporting SAEs, regardless of causal relationship, is as follows:

- Within 24 hours of the Site Investigator's knowledge of an SAE, the site must notify the Sponsor by phone call to their site monitor, medical monitor or other Sponsor representative. They should also immediately complete the AE eCRF and select "Serious".
- This initial reporting of an SAE should contain as much information as is available to the Investigator. Submission of the SAE via the EDC should not be delayed in order to collect additional information to complete the form.
- Follow-up SAE reports may be generated in cases in which additional information becomes available. Hospital records, autopsy reports, and other documents may become available and scanned copies can be provided to the Sponsor when applicable. The follow-up SAE report should describe whether the event has resolved or continues, if and how it was treated, whether the blind was broken or not, and whether the subject continued or withdrew from study participation.
- The Sponsor (or designee) will distribute completed SAE forms, which may be used to notify the IRB when applicable, via a secure internet-based document depository.
- The Site Investigator should notify the IRB of Serious Adverse Events occurring at the site and other adverse reports received from the Sponsor in accordance with reporting requirements of the governing IRB.

The Site Investigator must take all therapeutic measures necessary for resolution of the SAE. Any medications necessary for treatment of the SAE must be recorded onto the concomitant medication section of the subject's eCRF. However, treatment medication should only be recorded in the narrative description section of the SAE form.

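### AE and SAE rules depend on arm in a double-blind trial, and the TEAE window runs about 10 days past the end of required AE documentation

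*Combined protocol and SAP*

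**What the plan says.** **Blinding and dosing.** Section 3.1 describes a double-blind, placebo-controlled trial. Section 6.1 gives placebo on the same Day 1 to Day 10 schedule: "Subjects randomized to the placebo + SOC arm will be administered placebo BID".

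**AE start (8.4.3).** Events "that occur after dosing with favipiravir and after completion of baseline assessments in the Placebo + SOC arm, must be recorded as an AE". The two arms get different starting points.

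**SAE reporting (8.4.4).** SAEs that "occur after the first dose of favipiravir and up to 46 days post-dose must be reported to the Sponsor". The next sentence drops the drug name: "Any SAEs occurring more than 46 days after last study drug administration" must also be reported if at least possibly drug-related. Section 8.4.6 has no arm limit: "The procedure for reporting SAEs, regardless of causal relationship, is as follows".

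**Follow-up after withdrawal (8.4.1).** A subject withdrawn from the study because of an AE is "followed until the event has resolved or stabilized or 14 days after last dose, if in the" favipiravir arm. Section 8.4.3 sets a general rule without reference to arm: "The Site Investigator must follow all AEs until the AE resolves", or is judged chronic or stable.

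**TEAE window and collection.** Sections 8.4.1 and 9.7 define TEAEs from the start of treatment to 28 days post-treatment. Section 8.4.1 requires sites to document AEs through the Day 28 visit. That is the last visit in the Section 14 schedule, and Section 7.3 allows it one day either side. The Synopsis and Section 3.1 put each patient's participation at 28 days.

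**The concern.** Two things look wrong.

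First, a blinded site does not know which subjects are on favipiravir, so it cannot follow a recording start or a follow-up limit that depends on arm. Each site would have to choose its own rule. If the text were somehow applied literally, the arms would have different AE start points. Section 9.7 tabulates and compares all AEs by arm, not only TEAEs, so the difference could reach the analysis.

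Second, the TEAE definition appears to extend beyond the period in which non-serious events must be documented. SAEs stay reportable beyond Day 28 and, under 8.4.6, go on the same AE eCRF. The any-TEAE line in Section 9.7 would then cover one period for serious events and a shorter one for the rest.

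Safety and tolerability is a stated secondary objective, and Section 2.7 says the study will help define the safety profile, so what these tables cover matters.

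**Working it through.** **Arm wording.** The three rules side by side:

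| Rule | Favipiravir | Placebo |
|---|---|---|
| AE recording start (8.4.3) | after dosing | after baseline assessments |
| SAE reporting start (8.4.4, first sentence) | first dose | not named |
| 14-day limit after withdrawal (8.4.1) | applies | not named |

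The literal difference in AE start is the interval between the end of baseline assessments and the first dose. Its length is not stated. Sections 7.1 and 7.2 place both on Day 1, "with time 0 (time of first dose) occurring as quickly as possible after the" confirmation of eligibility.

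**TEAE gap.** The documents state no figure for this, so there is none to reproduce.

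Inputs: planned last dose on Day 10 (3.1, 6.1); TEAE window of 28 days post-treatment (8.4.1, 9.7); Day 28 visit on Days 27 to 29 (7.3). Assumption: post-treatment means after the last dose. The documents do not define it.

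- TEAE end = last dose day + 28 = 10 + 28 = Day 38.
- Gap = TEAE end − visit day: 38 − 28 = 10 days; 38 − 29 = 9; 38 − 27 = 11.
- Share of the 28 post-treatment days: 10/28 = 36% (9/28 = 32% to 11/28 = 39%).
- Share of Days 1 to 38: 10/38 = 26% (9/38 = 24% to 11/38 = 29%).
- Post-treatment days covered: 28 − 10 = 18 (17 to 19).

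**Subjects who stop drug early but stay to Day 28.** Last dose Day 5: 5 + 28 = Day 33, and 33 − 28 = 5 days (4 to 6 with the visit window). Last dose Day 1: 1 + 28 = Day 29, and 29 − 28 = 1 day (0 to 2). For subjects who leave the study, collection may end at the Early Termination visit in Section 7.3, so these figures do not apply to them.

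**Other reading of post-treatment.** Counted from the start of treatment, the window ends on about Day 29 (1 + 28), or on Day 28 if Day 1 is the first of the 28 days. With a visit on Day 28 the gap is then 1 day or none.

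**SAEs in the gap.** With last dose on Day 10, the 46 days end on Day 56 (10 + 46). Counted from the first dose they would end on Day 47 (1 + 46). Both are later than Day 38, so only new non-serious events fall in the gap. The post-study provision in 8.4.3 concerns AEs that are already open, not new ones.

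**The case against.** The other side has a good deal to say.

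- **The practical bias is small.** The unequal interval lies within Day 1, the safety population (9.4) is treated patients only, and TEAEs start with treatment in both arms. Section 8.4.3 also records onset date and timing relative to dosing, so pre-dose events could be identified. This stands. It does not remove the problem, because the comparison in 9.7 is of AEs generally.
- **Favipiravir may be shorthand for study drug.** That is plausible for 8.4.4. It does not work for 8.4.3, which gives both arms by name with different starts, or for 8.4.1, which singles out one arm.
- **A full SAP is to follow (Section 9).** It can redefine the window, but it cannot recover events that were never recorded.

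Some stronger readings are tempting, and the documents do not support them.

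- *Placebo SAEs go unreported.* Section 8.4.3 requires AEs and SAEs to be recorded in both arms, and 8.4.6 requires notification without an arm limit.
- *Late non-serious AEs are barred from collection.* Section 8.4.1 sets what must be documented through Day 28. It does not forbid recording a later report, and 8.4.3 gives no end date. The supportable statement is that documentation is not required.
- *The 46-day rule leaves a hole after Day 47.* That needs different starting points for two adjacent sentences. Read together, the second continues the first and both count from the last dose. A clarification is enough.
- *The 14-day clause has no practical effect because it expires before Day 28.* It concerns subjects withdrawn from the study, who have no assured Day 28 visit, so it may determine how long they are followed.

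**Conclusion.** The point holds at modest size. The AE start in 8.4.3 and the follow-up limit in 8.4.1 cannot be applied by blinded sites as written, and the first sentence of 8.4.4 needs the same correction. Any distortion of the by-arm AE comparison is probably small and cannot be quantified, because the length of the pre-dose interval is not given.

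For subjects who complete dosing, new non-serious AEs in about the last 10 days of the TEAE window (9 to 11) are not required to be documented, while SAEs in that period remain reportable. This rests on counting post-treatment from the last dose; counted from the start of treatment, the gap is about 1 day or none. It is shorter for those who stop drug early but stay to Day 28, and differs for those who leave the study.

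A reader might infer that the gap biases the comparison between arms. The documents do not support that: the TEAE window and the Day 28 limit are the same in both arms. The consequence is for what the any-TEAE summary covers.

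**What to change.** - **8.4.3 and 8.4.4:** use one arm-neutral start, namely after the first dose of study drug (favipiravir or placebo).
- **8.4.4, first sentence:** state that the 46 days run from the last study drug administration, matching the second sentence. This is a clarification only and does not shorten the reporting duty.
- **8.4.1:** reconcile the follow-up clause with 8.4.3 so that it does not depend on arm.
- **8.4.1 and 9.7:** define the window's starting point, and end the overall and non-serious TEAE summaries at the Day 28 visit to match collection. Report SAEs through 28 days after the last dose by arm in a separate, labelled summary. Without it, serious events on Days 29 to 38 would drop out of the between-arm comparison.

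The cost is text changes and one extra table. The downside is that the stated non-serious window becomes about 18 post-treatment days for completers (17 to 19) rather than 28. The alternative is to extend AE collection to Day 38. That would need one added contact per patient and a change to the 28-day participation in the Synopsis and Section 3.1.

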8.5 Suspected Unexpected Serious Adverse Reactions (SUSARs)

A SUSAR carries specific and time-based reporting requirements for the Sponsor of a clinical trial. Thus, after a Site Investigator reports an SAE, the FDA expects the Sponsor will determine whether it meets the definition of a SUSAR.

A SUSAR is defined according to 3 criteria:

1. The AE is deemed a "suspected adverse reaction" if there is a reasonable possibility that the study drug caused the AE. A "reasonable possibility" means there is evidence to suggest a causal relationship between the drug and adverse event.
2. The AE is "Serious" if it meets the definition of an SAE provided in section 8.4.5
3. The AE is deemed "unexpected" if it is not listed in the Investigator's Brochure (IB) or if in the IB, has not been reported at the severity observed.

In cases where the Sponsor deems a SUSAR has occurred, it must file an IND Safety Report with the FDA. FPHU will require the assistance and cooperation of the Site Investigator and staff to provide accurate and complete information on the subject and observed SAE so that reporting requirements to the FDA can be met.

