9.7 Safety Analysis

The frequency of adverse events and serious adverse events will be tabulated by type and by treatment arm. AEs will be compared by arm using the Chi-squared test or Fisher's exact test, as appropriate, in the safety analysis set.

The original exact terms in the electronic data capture (EDC) system used by Investigators to identify AEs other than symptoms of COVID-19 will be fully described and coded according to the Medical Dictionary for Regulatory Activities (MedDRA). Treatment-emergent AEs will be defined as those occurring coincident with start of treatment and through 28 days post-treatment. TEAEs will be summarized overall and by treatment group and by MedDRA body organ system and preferred term, severity, relatedness, and seriousness.

An overall summary of TEAEs will be presented by treatment, with subject counts and percentages of subjects with the event. This summary will include subjects with any TEAE, any treatment-related TEAE, any serious TEAE, any treatment-related serious TEAE, TEAEs leading to study infusion discontinuation, treatment-related TEAEs leading to study infusion discontinuation, TEAEs leading to death, and treatment-related TEAEs leading to death. The difference in proportions between treatment groups in each of these categories will be calculated.

Summaries of changes over time in laboratory parameters, as well as counts and percentages of laboratory parameters that are Low, Normal, and High compared to the reference ranges will be presented by treatment at each visit and time point. Shift tables will be presented for laboratory parameters with defined severity grades.

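### The two causality codes in 8.4.3 do not cover every adverse event and are narrower than the 8.5 standard, which leaves the treatment-related TEAE rows in 9.7 inconsistent and probably too low

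*Combined protocol and SAP*

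**What the plan says.** Section 8.4.3 says that relatedness "will be determined initially by the Site Investigator" and offers two categories.

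- 'Related' consists of three consecutive sentences with no AND or OR between them. The first is on timing: "There is a distinct temporal relationship between the event onset and administration of the study drug". The second asks for prior knowledge of such a reaction: "There is a known reaction to agent or chemical group or predicted by known pharmacology". The third excludes competing causes: "The event cannot be explained by subject's clinical state or other factors".
- 'Unrelated' reads "Evidence exists that the AE has an etiology other than the study drug", with examples that include the underlying disease.

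The Sponsor then makes the final determination. The section closes by calling the criteria a guide to be used with clinical judgement, and asks for an alternative explanation whenever an event is felt not to be related.

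Two other sections word causality differently. Section 8.5 treats an event as a suspected adverse reaction if "there is a reasonable possibility that the study drug caused the AE", and explains this as evidence suggesting a causal link. Section 8.4.4 requires SAEs more than 46 days after the last dose to be reported if a link to the drug is judged at least possible.

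Section 9.7 builds its TEAE summary on relatedness among other things, including "any treatment-related TEAE, any serious TEAE, any treatment-related serious TEAE", and calculates the between-arm difference in proportions for each category. It does not say whether the site's or the Sponsor's determination is used.

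**The concern.** A two-code scale should be exhaustive: whatever is not 'Related' should be 'Unrelated'. Here each code has its own positive requirements, so an event can fail both. The second and third statements under 'Related' are the demanding ones. The second asks for a reaction that is already known or can be predicted from pharmacology, which a wholly new effect does not satisfy. The third asks that nothing else explain the event, which is hard to satisfy when the trial disease shares symptoms with the drug's known reactions.

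At stake is what the treatment-related rows in 9.7 mean. Section 2.7 says the study should help define the safety profile in this setting, and a code that favours reactions already known works against that aim. With up to 5 sites (3.2), events that meet neither definition may also be coded differently from site to site.

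**Working it through.** No figure in the plan bears on this point, so there is nothing to recompute. The check sets the definitions side by side and runs typical events through them.

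**Inputs.** The two codes in 8.4.3; the reasonable-possibility standard and the definition of unexpected in 8.5 (not in the Investigator's Brochure, or not at the observed severity); the known reactions in 2.3 (raised uric acid and diarrhea are the two most common); and the COVID-19 symptom lists in 5.1 and 8.1, both of which include diarrhea.

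**Step 1: literal, cumulative reading of 'Related'.**

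| Well-timed event | Known or predicted? | No other explanation? | Evidence of another cause? | Code under 8.4.3 | Could meet 8.5? |
|---|---|---|---|---|---|
| Raised uric acid, nothing else to explain it | Yes | Yes | No | Related | Yes |
| Class effect absent from the Brochure, or known reaction at greater severity | Yes | Yes | No | Related (and unexpected) | Yes |
| Wholly novel effect, no other cause found | No | Yes | No | Neither | Yes |
| Diarrhea that COVID-19 might explain but is not shown to have caused | Yes | No | No | Neither | Yes |
| Event with a demonstrated other cause | Either | No | Yes | Unrelated | No |

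The third and fourth rows are the gap. Both could satisfy 8.5 and the 8.4.4 wording, and neither satisfies a code in 8.4.3.

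**Step 2: the other reading.** If any one of the three sentences were enough, good timing alone would make an event 'Related'. Rows three and four would then be 'Related', and a well-timed event with a demonstrated other cause would meet both definitions. The gap becomes an overlap. The text does not settle which reading applies, so two sites could code the same event in opposite ways.

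**Step 3: where relatedness is used.** The 9.7 summary lists eight categories: any TEAE, serious TEAEs, TEAEs leading to discontinuation and TEAEs leading to death, each overall and again restricted to treatment-related. So 8 / 2 = 4 rows, and their between-arm differences, depend on the code. The breakdown of TEAEs by relatedness depends on it too. The AE and SAE tabulations by arm, and the Chi-squared or Fisher's exact comparison of AEs, do not.

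**Step 4: reporting of SAEs.** Up to 46 days post-dose, 8.4.4 and 8.4.6 send SAEs to the Sponsor whatever their presumed cause, and the Sponsor applies 8.5. The site's code controls nothing there. After 46 days, reporting depends on a causality judgement. If that judgement follows 8.4.3, a late novel SAE might not be reported. TEAEs end 28 days post-treatment, so this is a reporting issue and does not touch the 9.7 tables.

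**The case against.** The strongest reply is that the criteria are expressly a guide, to be combined with clinical judgement, and that the Sponsor has the last word. Nothing forces a site to refuse the 'Related' code. A reader might infer that a new effect can never be classed as related; that sentence, and the absence of any connective in the definition, do not support so firm a claim.

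A reader might also infer that the definition shuts out unexpected reactions and so defeats SUSAR detection. It does not. It admits reactions predicted by known pharmacology, and an unlisted class effect or a known reaction at greater severity can be both unexpected and 'Related'. Within 46 days post-dose, the trigger for Sponsor review is seriousness, not the site's causality code.

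The undercount, too, is not demonstrated. An ambiguous event fails 'Unrelated' as well, so judgement could place it in either code. Raised uric acid is not obviously explained by COVID-19, and some subjects enter without symptoms, so 'Related' remains reachable. Section 8.4.2 keeps COVID-19 progression out of the AEs and 9.7 codes AEs other than COVID-19 symptoms, so some diarrhea may never reach the relatedness field.

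These points narrow the concern but do not close the gap. Clinical judgement supplies no third code and no common rule across sites. The Sponsor's final determination has no stated standard outside the SUSAR route, which leaves non-serious events to the 8.4.3 wording. And 9.7 does not say whose determination it tabulates.

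**Conclusion.** The definitions in 8.4.3 are not exhaustive when read literally, and they are narrower than the standards in 8.5 and 8.4.4. The exposed parts are the four treatment-related rows of the 9.7 summary with their between-arm differences, and SAE reporting after 46 days. The all-cause safety comparisons stand, as does SUSAR review up to 46 days.

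The size cannot be estimated: the documents give no rate of novel or ambiguous events and no rate of Sponsor reclassification. That the counts are probably too low rests on two assumptions: that sites read the three statements as cumulative, and that they default to 'Unrelated' when those are not all met. If sites differ on either, the result is inconsistency with no sure direction. Drug-caused events that go uncoded as related would come from the favipiravir arm, so losing them would shrink the between-arm difference in those rows.

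**What to change.** In 8.4.3, define 'Related' as a reasonable possibility that study drug caused the event, using the explanation already given in 8.5, and 'Not related' as no reasonable possibility. Every event then has exactly one code. Timing, known pharmacology and alternative explanations can stay as factors to weigh, not conditions to meet. Use the same wording in 8.4.4 for SAEs after 46 days. In 9.7, state that the treatment-related rows use the Sponsor's final determination under this standard.

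The cost is a few sentences, with no change to visits, sample size or the statistical tests. The downside is that somewhat more events will be labelled related in both arms. That is tolerable in a placebo-controlled trial, because the comparison between arms shows how much of that labelling is background.
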